37 outcomes will be compared with those of transplant candidates who are evaluated for but
38 do not receive LDLT. The primary objective concerns comparison of morbidity and
39 mortality of patients who receive LDLT with a group or groups of patients with similar
40 illnesses and prognoses. It is also important to compare the outcomes after LDLT to
41 those after cadaveric transplantation. Transplant physicians need this information on
42 outcomes to advise patients and prospective donors. Therefore, sufficient patient and
43 donor pairs will be recruited to determine whether recipients of LDLT have substantially
44 different survival than non-LDLT recipients. A large number of donors and recipients

45 from several geographically distributed institutions will be necessary to reliably
46 determine if outcomes are different with the two approaches.

47
48 These issues are best addressed through prospective data collection. But, the main
49 outcomes of the A2ALL prospective data collection will not be available for at least 5
50 years. Therefore, to gain initial insights into outcomes associated with these procedures,
51 a retrospective cohort or look back study has been designed to compare the outcomes of
52 LDLT and cadaveric liver transplants and the outcomes for living liver donors beginning
53 in 1998 at the nine participating transplant centers of the A2ALL study. In order to be
54 conducted rapidly and efficiently, this study will rely exclusively on existing medical
55 records and patient materials.

56 **3. Study Objectives/Specific Aims**

57 **3.1. Overall Aim of the Retrospective Cohort Study**

58 The primary study objective is to determine whether the *decision* to undergo LDLT is
59 beneficial for the patients who choose LDLT. The principal hypothesis is that receipt of
60 a living liver allograft leads to better long term outcomes for liver transplant candidates
61 than *pursuit* of cadaveric transplant. This is a study of the decision to perform LDLT.
62 Several different patient outcomes will be considered.

63 **3.2. Comparison of mortality between LDLT and non-LDLT recipients**

64 **3.2.1. Primary Aim**

65 To compare the survival distribution from time of identification of a potential living
66 donor between those receiving an LDLT and those not receiving one.

67 **3.2.2. Secondary Aims**

68 To compare the survival of LDLT vs. cadaveric recipients from time of transplant.

- 69

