302 evaluated for LDLT, and were alive and eligible for transplant at the same time following
303 donor evaluation as the LDLT patient was when they received their transplant. This
304 analysis will involve a different set of controls for each patient, with many control
305 patients re-used in several control sets. A modified Cox regression will be performed,
306 with statistical adjustment for the re-use of controls. In both Cox analyses, variables will
307 be checked to ensure that the proportional hazards assumption is met. If non-proportional
308 hazards are detected, particularly for the LDLT effect, they will be modeled using time-
309 dependent covariates. Interactions between covariates and the LDLT effect will be
310 tested.

311
312 Survival from date of surgery for LDLT versus cadaveric transplant will also be
313 compared using Cox regression, adjusted for prognostic variables. The distributions of
314 time from transplant to rejection episode between LDLT and cadaveric transplant will be
315 similarly compared.

316
317 We will also analyze the incidence, timing, and diagnosis (biopsy-proven or not) of
318 clinically evident liver transplant rejection requiring treatment. Analyses of rejection will
319 include subsets restricted to biopsy-proven and steroid-resistant rejection episodes.

320 **4.3. Study of Hepatitis C Virus Infection**

321 **4.3.1. Study Methods**

322
323 LDLT recipients transplanted for HCV will be compared to an approximately equal
324 number of contemporaneous cadaveric controls selected from SRTR based on a diagnosis
325 of HCV. If SRTR data are not complete for HCV identification, identification of HCV
326 patients at the facility level may be required.

327 (Note: Post-transplant biopsies will be re-read by the local pathologist for grade, stage,
328 and other characteristics of recurrent HCV. The biopsy performed closest to the one-year
329 anniversary of transplant (+/- 3 months) will be employed for histologic scoring)

330

331 Primary end-point

332

333 a) Severity of disease based upon Knodell (necroinflammatory) and Ishak
334 (fibrosis) scores on liver biopsy at 1 year (\pm 3 months) post-transplant in LDLT
335 and cadaveric transplant.

336

337 Secondary end-points

338

339 a) Rate of fibrosis progression (comparison of 0, 1 year and most recent biopsy
340 [the latter must be a minimum of 12 months after the 1-year biopsy] in LDLT
341 and cadaveric transplants)

342 b) Proportion with cholestatic hepatitis

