
343 c) Proportion with treated acute rejection episodes

344 d) Graft loss due to recurrent hepatitis C

345 **4.3.2. Participant Selection**

346 All right lobe LDLT patients age \geq 18 with documented positive HCV RNA prior to
347 transplantation whose donors were evaluated between 1/1/1998 and the start date of
348 enrollment into the A2ALL-Cohort-01 Study, and excluding those receiving anti-HCV
349 positive or anti-HB_c positive organ. Cadaveric transplant controls transplanted for
350 hepatitis C will be identified from cadaveric transplant controls in the retrospective study.
351 Additional HCV-infected cadaveric transplant recipients will be identified by SRTR if
352 there are insufficient matched controls in the retrospective study population. The
353 analysis will adjust for center and time of transplant (both calendar time and time from
354 donor identification).

355

356 Inclusion criteria

357

358 a) LDLT patients and cadaveric transplant patients with HCV

359 b) HCV RNA positive (within 12 months if no antiviral therapy or if HCV RNA
360 positive post-transplant)

361

362 Exclusion criteria (cases and controls)

363

364 Anti-HCV positive controls who received anti-HB_c positive or anti-HCV positive organs.
365 Patients who are HCV RNA negative at last assessment prior to the time of transplant

366

367 Controls will be selected as above.

368 **4.3.3. Data Elements**

369 Verification of diagnosis with report of positive HCV RNA either pre- or post-transplant.

370 Identification of anti-HB_c and anti-HCV status for both donor and recipient.

371
372 Histology 1 year post-transplant (\pm 3 mos), at start of antiviral therapy (if on treatment),
373 and at last histological follow-up.
374
375 Data elements (donor and recipient) that will be collected for the retrospective study, plus
376 the following:
377
378 Pre-transplant:
379
380 • HCV RNA level pre-transplant (within 12 months of transplant and in whatever units
381 available – IU/mL preferred).
382 • HCV genotype
383 • History of antiviral therapy for hepatitis C prior to transplant (start and stop dates,
384 specific therapy used, treatment response [ETR, SVR])
385 • HBV markers in recipient
386 • Graft size
387 • Donor age, BMI, steatosis, DM
388
389 Post-transplant (immunosuppressive therapy, treatment of rejection and other data
390 collected as part of retrospective study)
391 HCV RNA levels at 1 year \pm 3 months, at time of onset of cholestatic hepatitis, at time of

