392 re-transplant)
393
394 ALT levels (liver panel) within one month of transplant and at 1,3,6,9 and 12 months post
395 transplant.
396 Antiviral treatment (start and stop dates, specific drugs and doses used and response
397 [ETR, SVR])
398
399 Pre-transplant and post transplant treatment in both groups
400
401 HLA matching with donor
402
403 Pathology interpretation: Re-review by local pathologist and scoring using Knodell
404 (necroinflammatory) and Ishak (fibrosis) scores.
405
406 Working definition of cholestatic hepatitis:
407 1. Bilirubin \geq 4 mg/dl x 2 wks minimum, at least 8 weeks post-transplant, PLUS .
408 2. Pathology features of
409 (i) cholestasis
410 (ii) lobular or portal inflammation
411 (iii) absence of features of acute rejection and chronic rejection. PLUS
412 3. Absence of the following:
413 • hepatic artery thrombosis
414 • biliary stricture
415 • sepsis

416 **4.3.4. Sample Size and Power Calculations**

417 Primary endpoint: Comparison of Knodell (necroinflammatory) and Ishak (fibrosis)
418 scores in LDLT or cadaveric transplant at 1 year post-transplant. Predictors of disease
419 severity will be investigated using ordinal logistic regression analysis. We anticipate
420 having at least 300 LDLT recipients and 250 cadaveric recipients, but only about 1/3 of
421 these will have HCV prior to transplant. We assume sample sizes of 100 LDLT and 83
422 cadaveric recipients with prior HCV. Because sample size calculations for ordinal
423 logistic regression are difficult, we base power calculations on a two-sample t-test (2-
424 sided, $\alpha=0.05$). For fibrosis score (0 to 6) as an outcome variable, we have 91%
425 power to detect a difference of 0.5 in fibrosis score between LDLT and cadaveric
426 recipients, assuming a standard deviation of 1.0.

427
428 Secondary endpoints: To compare rate of fibrosis in LDLT and cadaveric transplants
429 (use last available biopsy). All biopsies scored for fibrosis using Ishak (0-6) and rate is
430 based on time between transplant and last available biopsy. For the presence of severe
431 histologic fibrosis at 1 year, we expect approximately 10% overall with bridging fibrosis
432 (Ishak \geq 3). We will have 83% power to detect proportions as different as 0.05 for
433 cadaveric transplant and 0.20 for LDLT, based on a chi-square test of equality of
434 proportions with $\alpha=0.05$.

435
436 We consider the power for comparing time to graft loss due to HCV based on a logrank

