437 test with $\alpha=0.05$. We will have 84% power to detect a difference in the probability of
438 graft loss at one year as large as 15% for LDLT versus 5% for cadaveric recipients.
439

440 **4.3.5. Statistical Analysis**

441 Fibrosis score will be analyzed using both ordinal and ordinary regression analyses, with
442 the LDLT versus cadaveric recipients as the variable of primary interest. Ordinal logistic
443 regression will be used to accommodate the ordinal nature of the fibrosis scale. Ordinary
444 regression analysis will supplement the ordinal analysis and will facilitate interpretation,
445 but does assume that the ordinal scale has roughly equal increments.

446 The proportions of patients with fibrosing cholestatic hepatitis and treated acute
447 rejection episodes will be analyzed using chi-square tests of equality of proportions
448 between LDLT and cadaveric groups. Logistic regression will be used to compare LDLT
449 versus cadaveric transplants, adjusted for other covariates. Finally, time to graft loss will
450 be analyzed using Cox regression, again comparing LDLT versus cadaveric recipients
451 and adjusting for other prognostic factors. Graft loss or death due to causes other than
452 HCV will be censored.

453 **4.4. Study of Hepatocellular Carcinoma**

454 **4.4.1. Study Methods**

455 LDLT recipients transplanted for HCC will be compared to HCC patients who had a
456 donor evaluated for possible LDLT but who did not receive a LDLT. The analysis will
457 adjust for cirrhosis etiology diagnosis, center, age, CTP/MELD score, use of ablation
458 pretransplant, and pre transplant ablation method (i.e. chemoembolization, RFA, etc.). In

459 addition, a comparative analysis of LDLT and cadaveric transplant patients with HCC
460 will be conducted.

461 **4.4.2. Participant Selection**

462 All right lobe LDLT patients age ≥ 18 whose donor was evaluated between January 1,
463 1998 and the start date of enrollment into the A2ALL-Cohort-01 Study at one of the
464 A2ALL transplant centers, with patient diagnosis either primary or secondary of cirrhosis
465 and HCC. Excluded subjects include any patient who was transplanted with a
466 preoperative diagnosis of HCC and cirrhosis where no HCC was found at explant
467 histology, and no prior ablation is recorded that may have caused complete necrosis of
468 tumor leading to pathologic disappearance. For the comparative study of LDLT and

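### The HCV analysis adjusts for a time covariate that SRTR-added controls generally lack, and its 91% power assumes that every recipient has a biopsy at 9 to 15 months

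*Protocol*

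**What the plan says.** **Endpoint.** The primary HCV endpoint in Protocol 4.3.1 is the Knodell and Ishak "fibrosis) scores on liver biopsy at 1 year", give or take 3 months. Biopsies are re-read locally for grade, stage "and other characteristics of recurrent HCV. The biopsy performed closest to the one-year" "anniversary of transplant (+/- 3 months) will be employed for histologic scoring". No biopsies are taken for the study. Section 2 says that, to be "conducted rapidly and efficiently, this study will rely exclusively on existing medical" records and patient materials.

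**Power.** Section 4.3.4 takes one third of 300 LDLT and 250 cadaveric recipients: "these will have HCV prior to transplant. We assume sample sizes of 100 LDLT and 83" cadaveric. With a two-sided t-test at 0.05, a difference of 0.5 and an SD of 1.0, it states 91% power. The same section gives, for the secondary graft-loss endpoint, 84% power for a difference in the probability of "graft loss at one year as large as 15% for LDLT versus 5% for cadaveric recipients".

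**Controls and adjustment.** Section 4.3.2 takes cadaveric controls from the retrospective study first. "Additional HCV-infected cadaveric transplant recipients will be identified by SRTR if" matched controls there are too few. The next sentence says the "analysis will adjust for center and time of transplant (both calendar time and time from" donor identification).

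**The concern.** **The covariate.** Section 4.1 defines cohort entry by the evaluation of a potential living donor. Supplementary SRTR controls come from outside that cohort, so they generally have no date of donor identification. A model with that covariate cannot be computed for the very patients brought in to fill the control group. Section 4.3.1 widens the problem, because it describes the controls as drawn from SRTR by HCV diagnosis.

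**The denominator.** A graft or patient lost before month 9 cannot have a biopsy in the window. A surviving patient who was not biopsied in clinical care at that time has none either. The power statement allows for neither.

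**Selection.** Some early losses are caused by the disease being scored. If these are more frequent after LDLT, the histology comparison understates how severe recurrence is after LDLT, which is the question of the primary aim in 3.3.1. A larger sample would not remove that bias.

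**Working it through.** **1. Reproduce the stated power.** Inputs from 4.3.4: n = 100 and 83, difference 0.5, SD 1.0, two-sided alpha 0.05. Noncentrality = 0.5 × √(100 × 83 / 183) = 3.37. Noncentral t with 181 df gives 0.918, and the normal approximation gives 0.920. The stated 91% is reproduced, but only with every patient scored.

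**2. Fewer scored patients, no selection.** Same formula with smaller n.

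| Lacking a window biopsy (LDLT / cadaveric) | Scored | Power |
|---|---|---|
| none | 100 / 83 | 0.92 |
| 15% / 5% | 85 / 79 | 0.89 |
| 30% / 30% | 70 / 58 | 0.80 |
| 40% / 40% | 60 / 50 | 0.73 |
| 50% / 50% | 50 / 41.5 | 0.65 |

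The 15%/5% row borrows the detectable alternative in 4.3.4 as an illustration. The other rows are assumptions, since the protocol gives no biopsy rate.

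**3. Controls without the covariate.** Appendix A counts 181 cadaveric recipients among the candidates. One third is 181/3 ≈ 60, against 83 in the power statement. The gap is 83 − 60.3 ≈ 23, or 27% of the controls. If patients without the covariate are dropped, 100 versus 60 gives noncentrality 3.06 and power 0.86. Combined with the 15%/5% loss (85 versus 57), power is 0.83. The gap closes if enough of the 239 candidates still waiting receive a cadaveric graft: 250 − 181 = 69, and 69/239 = 29%.

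**4. Direction and possible size of the selection bias.** Suppose fractions l (LDLT) and c (cadaveric) are lost, and the lost grafts would have scored k SD above their arm mean. The observed difference is then 0.5 − k·l/(1 − l) + k·c/(1 − c). With l = 0.15 and c = 0.05 this is 0.5 − 0.124k: 0.44, 0.38 and 0.31 for k = 0.5, 1.0 and 1.5.

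The extreme case removes exactly the highest scores in each arm (truncated normal, with the SD shrinking accordingly).

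| Lost (LDLT / cadaveric) | Observed difference | Power |
|---|---|---|
| 15% / 5% | 0.33 | 0.71 |
| 10% / 5% | 0.41 | 0.86 |
| 7.5% / 5% | 0.46 | 0.92 |
| 5% / 5% | 0.50 | 0.95 |

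In this model equal loss leaves the difference unbiased. The bias depends on a difference in loss between the arms, which the protocol does not estimate.

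**The case against.** **The 15% versus 5% is not a forecast.** It is the difference the graft-loss test could detect. The protocol nowhere predicts three times as many HCV graft losses after LDLT. This stands, so those figures serve only as an illustration.

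**Early losses need not carry the highest fibrosis scores.** The working definition of cholestatic hepatitis in 4.3.3 rests on bilirubin, cholestasis and inflammation, not on fibrosis stage. Grafts lost between months 9 and 12 may also have a usable biopsy. Both points stand, so a reader who infers that true power is about 70% goes beyond the documents.

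**Lost grafts remain in the HCV study.** Graft loss due to HCV is a secondary endpoint with its own power statement and Cox analysis, and 4.3.4 plans a fibrosis rate up to the last available biopsy. This is correct, but neither changes the denominator of the primary comparison or any bias in it.

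**Missing biopsies and covariates may be handled in an analysis plan that is not shown.** That is fair for methods, and the protocol states no complete-case rule. But the sample size behind the 91% and the named covariate are set in this protocol.

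**Supplementation is conditional.** It happens only if cohort controls are too few, and 181 is not a final count. The same table has 335 LDLT recipients, and 335/3 ≈ 112 versus 60 gives power between 0.87 and 0.88. This limits the size of the covariate problem but does not define the covariate for any control who is added.

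**Conclusion.** The point holds in three limited parts.

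1. The covariate in 4.3.2 is generally undefined for SRTR-added controls, so the adjusted model as written cannot include them. Power would be about 86% if about 23 of the 83 controls were added ones and were dropped. That rests on 181 being final and on a one-third HCV share. The defect is one of wording, and even this power stays above 80%.
2. The 91% is arithmetically right but conditional on complete biopsy availability. It becomes about 89% under the 15%/5% illustration, and about 80% if 30% of both arms lack a biopsy.
3. HCV-related loss before the window can bias the histology comparison toward no difference if it is heavier after LDLT. The direction follows from the design, but the size is unknown.

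Two stronger readings are tempting. One is that the worst outcomes will leave mainly the LDLT arm and cut power to about 70%. That needs a detectable alternative to be read as the expected rate and exactly the worst scores to be lost. The other is that the primary endpoint must become a composite. The primary aim is explicitly histological, and making graft loss or death part of it would change the question.

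**What to change.** - **4.3.2:** in any comparison that includes added SRTR controls, adjust for a time measure defined for everyone, for example listing to transplant (listing date is already collected under 4.2.3). Keep time from donor identification for an analysis restricted to cohort patients. The two measure different things, so the second analysis preserves the adjustment now stated. Reconcile the sources of controls in 4.3.1 and 4.3.2.
- **4.3.4:** restate power for the number expected to have a biopsy in the window, with the assumed availability given.
- **4.3.5:** keep histology as the primary endpoint and report biopsy availability by arm. Add a sensitivity analysis in the planned ordinal logistic model with HCV-related graft loss, retransplant or death before the biopsy as the worst category.

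Graft loss, retransplantation, death and listing date are already planned data, so no new collection is needed. The cost is a little more analysis, a sensitivity outcome that mixes histology with graft loss, and a slightly lower stated power.

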469 cadaveric transplant recipients, no supplemental contemporaneous cadaveric controls will
470 be used.

471 **4.4.3. Data Elements**

472 Maximum size and number by radiology pre-transplant and at transplant (explant)
473 Whether Milan criteria were met
474 Whether HCC was an incidental finding.
475 Date of diagnosis of disease recurrence post-transplant.
476 Number and type of HCC ablation procedures.

477 **4.4.4. Sample Size and Power Calculations**

478 We anticipate approximately 75 hepatocellular carcinomas among the ~ 300 LDLT cases,
479 and approximately 125 among the ~ 500 non-LDLT cases who were also evaluated for
480 LDLT. With 75 LDLT cases and 125 non-LDLT cases, we will have 90% power to
481 detect a difference in recurrence (or presence) of HCC of 10% versus 30%. Since
482 reduction of HCC in the non-LDLT group will be due to subsequent cadaveric
483 transplantation, this statistical test will compare the strategy of LDLT versus waiting for a
484 cadaveric transplant.

485 **4.4.5. Statistical Analysis**

486 Initial analysis of HCC will be primarily descriptive. The characteristics of HCC patients
487 described will include TNM explant pathologic stage, use of ablation pretransplant, and
488 pre transplant ablation method (i.e. chemoembolization, RFA, etc.). The proportion
489 recurring within one year will be presented, with 95% CI. Predictors of one-year
490 recurrence will be explored using logistic regression for patients with at least one year of
491 follow-up. The difference between recurrence (or presence) proportions for LDLT versus
492 non-LDLT patients will also be estimated using a 95% confidence interval. A comparison
493 of survival between these two groups will be performed using Cox regression, adjusted
494 for various prognostic covariates. A comparison of survival between LDLT and
495 cadaveric transplant recipients will also be performed.

496 **4.5. SRTR Data Validation Study**

497 *(This section does not apply to subjects who have the first living donor evaluated after*
498 *2/28/03)*

499 **4.5.1. Study Methods**

500 We will investigate records for all patients with LDLT, and a subset of patients not
501 receiving LDLT. These patients will be selected as needed to develop comparison
502 cohorts for the other Retrospective research aims. All patients to be studied as part of
503 any Retrospective cohort will be included in this validation study.

504

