571 medical groups including visits to the emergency room department at other hospitals will
572 be documented. Also, any subsequent medical care, such as physical therapy, will also
573 be noted. It is the intent of this process to be inclusive of all potential complications that
574 either required intervention or continuous monitoring. No control group will be used.
575

576 For the study of recipient complications, treated post-transplant complications (bile leaks,
577 re-operation, treated rejection, and treated CMV infection) will be examined. The
578 recipient complications study will focus on post-operative complications requiring
579 intervention.

580 **4.6.2. Participant Selection**

581 All donors who were evaluated for right hepatic lobectomy between 1/1/1998 and the
582 start date of enrollment into the A2ALL-Cohort-01 Study at any of the nine A2ALL
583 centers and subsequently underwent the procedure will be included. All waitlisted

584 candidates for liver transplantation who had a potential donor considered for living donor
585 transplantation and subsequently underwent either an LDLT or cadaveric transplant will
586 be included. Supplementation of contemporaneous controls above those identified in the
587 cohort component of the study may be necessary. If additional patients are needed, they
588 will be selected using SRTR data. Controls will be frequency matched on center and date
589 of transplantation (6 month window). In analysis, we will control for these variables as
590 well as age, sex, disease (HCC, cholestatic, HCV/HBV, alcoholic, other), and severity of
591 illness (MELD score, OPTN/UNOS status).

592 **4.6.3. Data Elements**

593 Data elements for the donor morbidity study will be taken from a donor
594 morbidity/outcomes worksheet. Data elements for the comparative study of recipient
595 morbidity will be taken from a recipient morbidity data collection form.

596 **4.6.4. Sample Size and Power Calculations**

597 Estimation of proportions of donor complications will be made using 95% confidence
598 intervals (CI) based on the binomial distribution. Assuming 300 donors, 95% CI widths
599 will be no larger than +/- 0.057.

600
601 Comparisons of recipient complications after LDLT and cadaveric transplants will be
602 based on chi-square tests of equality of proportions. Assuming $n=300$ LDLT, $n=250$
603 cadaveric, and $\alpha=0.05$, we will have 89% power to detect a difference in the

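### Cholestatic hepatitis in the HCV study is a crude proportion with no upper time limit, tested by chi-square and logistic regression without allowance for follow-up

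*Protocol*

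**What the plan says.** - **Endpoint (4.3.1).** The second HCV secondary endpoint is "Proportion with cholestatic hepatitis". No period is attached.
- **Definition (4.3.3).** Bilirubin must stay raised for at least two weeks, "at least 8 weeks post-transplant", with histological features and exclusions. There is no latest time.
- **Test (4.3.5).** "The proportions of patients with fibrosing cholestatic hepatitis and treated acute" "rejection episodes will be analyzed using chi-square tests of equality of proportions" between LDLT and cadaveric recipients. A logistic model with covariates follows. Neither has a minimum follow-up, a follow-up term or censoring.
- **Graft loss, same paragraph.** This is a time-to-event outcome that will "be analyzed using Cox regression, again comparing LDLT versus cadaveric recipients", with other causes of graft loss or death censored.
- **Follow-up elsewhere.** The HCC analysis in 4.4.5 ("Predictors of one-year" recurrence) is limited to patients with at least one year of follow-up. Section 4.2.5 compares time to rejection in the same way as survival.
- **Entry and data source.** Donor evaluations start on 1/1/1998 and end on 2/28/03 (4.1) or at a site-specific later start of the prospective study (4.2.2). Section 2 limits the study to existing records. No record cut-off date is given.
- **Controls and adjustment.** Section 4.3.1 takes contemporaneous HCV controls from SRTR. Section 4.3.2 takes cohort controls first and supplements from SRTR if they are too few. It also adjusts for center, calendar time of transplant and time from donor identification.

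**The concern.** Aim 3.3.2 asks whether cholestatic hepatitis occurs at a higher rate after LDLT. A proportion of patients ever affected answers this only if everyone is observed over the same period. Here one recipient may have four years of records and another two months, and both enter with equal weight. On the natural reading of the definition, an event cannot be confirmed before about week 10. Anyone who dies, is regrafted or runs out of records before then sits in the denominator as a non-case.

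Two things are at stake. First, the reported percentage has no stated risk period, so it cannot be quoted to patients or compared with other series. Second, if the arms differ in follow-up, the chi-square test partly compares follow-up. The calendar-time adjustment in 4.3.2 can reach the logistic model. It does not reach the unadjusted test or the reported proportions, and it does not deal with early death or graft loss.

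**Working it through.** **1. The plan's own figures.** The protocol gives no power or expected rate for cholestatic hepatitis. Its nearest figures, for one-year rejection in 4.2.4, reproduce. With power = Φ[(|d| − 1.96·s0)/s1], n = 300 v 250 and 25% v 32%: pooled p = 155/550 = 0.2818, s0 = 0.03853, s1 = 0.03867, so power = Φ[(0.07 − 0.0755)/0.03867] = 44.3% (stated 44%). For 21% it is 83.3% (stated 83%). The stated power is not the problem.

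**2. Earliest observable event.** 8 weeks + 2 weeks = week 10, or week 8 if the two weeks may begin earlier. The calculations in steps 3 and 5 use week 8, which is the milder choice.

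**3. How the crude proportion depends on follow-up.** Assume a 10% one-year risk with a constant hazard from week 8 (assumptions, not in the protocol). Then λ = −ln(0.90)/(1 − 8/52) = 0.1054/0.8462 = 0.1245 per year, and the proportion seen by time t is 1 − exp[−λ(t − 8/52)].

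| Follow-up | Proportion seen |
|---|---|
| 0.5 y | 4.2% |
| 1 y | 10.0% |
| 2 y | 20.5% |
| 3 y | 29.8% |

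The same risk process gives 4% or 30% depending only on length of records. The crude figure can fall below or rise above the one-year risk.

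**4. Is unequal follow-up plausible?** Appendix A, by year of evaluation: 1998, 27/335 LDLT (8.1%) v 4/181 cadaveric (2.2%); 2002, 94/335 (28.1%) v 61/181 (33.7%). Before any supplementation, cadaveric recipients were evaluated somewhat later.

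**5. Effect on the chi-square test under equal true hazards.** Inputs: Appendix A counts; n = 100 v 83 (4.3.4); the step 3 hazard. Assumed: evaluations uniform within the year, LDLT 0.1 y after evaluation, cadaveric transplant 0.1 to 0.75 y after, and two record cut-offs. Ranges follow the cadaveric wait from 0.1 to 0.75 y.

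| | Cut-off Feb 2003 | Cut-off Jan 2004 |
|---|---|---|
| Mean follow-up, LDLT v cadaveric | 2.03 v 1.78–1.19 y | 2.87 v 2.62–1.97 y |
| No window: crude proportions | 19.8% v 17.5–11.7% | 27.7% v 25.7–19.4% |
| No window: false-positive rate | 6.6–31% | 6.0–26% |
| Risk ends at 1 y: crude proportions | 8.6% v 8.3–6.2% | 10.0% v 10.0–8.9% |
| Risk ends at 1 y: false-positive rate | 5.0–9.0% | 5.0–5.6% |

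A later cut-off does little for the open-ended endpoint. Confining it to one year removes most of the distortion, and censoring deals with the rest. With equal follow-up the rate stays at 5%.

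**6. Does the direction hold once controls are added?** The plan expects about 250 cadaveric recipients (4.1), but Appendix A has 181, leaving 69. Under a separate set of assumptions (5% per year from week 10, mean wait 3 months to LDLT and 6–9 months to cadaveric transplant, cut-off Feb 2003), the crude proportions are 8.0% LDLT v 6.2–5.7% cadaveric, a ratio of about 1.3 to 1.4. Suppose the 69 were transplanted evenly over 1998–99. Their mean time at risk is 2003.16 − 1999 − 0.19 = 3.97 y, so their proportion is about 1 − exp(−0.05 × 3.97) = 18.0%. The mixed control figure becomes (181 × 6.2% + 69 × 18.0%)/250 = 9.5%, a ratio of 8.0/9.5 = 0.85. Other placements of the 69:

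| Placement | LDLT/cadaveric ratio, Feb 2003 |
|---|---|
| None added | 1.29–1.41 |
| 1998–99 or 1998–2000 | 0.85–0.94 |
| 1998–2001 | 0.97–1.02 |
| Matched to LDLT transplant dates | 1.20–1.27 |

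The sign depends on which controls are added.

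**The case against.** A reader might infer three stronger points, and the protocol does not support them.

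- **That LDLT has the longer follow-up and will look worse.** Appendix A alone suggests it. But 4.1 expects augmentation mainly for a program's first one to two years, where cohort controls are sparse, and 4.3.1 draws contemporaneous controls from SRTR. Step 6 shows that the imbalance may shrink or reverse.
- **That every post-transplant complication is affected.** Section 4.6.4 does plan power "based on chi-square tests of equality of proportions. Assuming" stated sample sizes, but the analysis section, 4.6.5, assigns logistic, Cox or ordinary regression by outcome type, so time-to-event complications already have Cox regression. Treated rejection is collected within one year of transplant (4.2.3) and has a time-to-event comparison in 4.2.5. What remains there is only recipients with under a year of records.
- **That rates are always understated.** They are understated relative to complete follow-up, but step 3 shows that an open-ended proportion can exceed the one-year risk.

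It can also be said that evaluability and early deaths belong in an analysis plan that is not shown. That is fair for a missing denominator rule. It does not answer the point, because the protocol itself fixes the endpoint as a plain proportion and names the test. The exclusions in 4.3.2 concern HCV RNA and donor serology, not follow-up. Finally, the Feb 2003 cut-off is the harshest case: the fibrosis endpoint needs biopsies well beyond one year, so a later cut-off is likely.

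**Conclusion.** The point holds for cholestatic hepatitis. As written, the endpoint has no defined risk period, and its unadjusted test mixes risk with length of follow-up. This follows from the text and needs no simulation. A bias between arms is conditional: it arises only if follow-up differs, its direction cannot be settled from the protocol, and equal follow-up would produce none. The false-positive rates of 6% to 31% (no window) and 5% to 9% (events confined to year one) rest on assumed cut-offs, waits and hazards and on Appendix A controls without supplementation, so they are illustrative only. One named secondary aim is affected; the primary endpoints and stated power figures are not. It should be corrected because the comparison concerns a possible harm of LDLT and the remedy is already in the same paragraph.

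**What to change.** In 4.3.5, replace the chi-square test on the crude proportion of cholestatic hepatitis with the following:

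- Time from transplant to first onset, within a fixed first post-transplant year.
- Censoring at the end of each recipient's records, with death and retransplantation as competing events.
- One-year cumulative incidence by arm, with confidence intervals.
- Comparison of arms by cause-specific Cox regression with the 4.3.2 adjustments, in line with the graft-loss analysis.

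State the one-year window in 4.3.1 as well. For treated rejection in the HCV subset, use the one-year time-to-event analysis already in 4.2.5. Section 4.6 needs no change beyond applying the Cox option that 4.6.5 gives.

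The cost is wording, plus an onset date and an end-of-records date per recipient. Section 4.3.3 already asks for HCV RNA at onset of cholestatic hepatitis, so onset has to be identified anyway. The small downside is that events after one year drop out of this comparison; they can still be described.
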